1. To determine if ACT enhances response to a high-magnitude CM procedure targeting cocaine-negative urines. It is hypothesized that initial treatment (4 weeks) with ACT and CM (ACT+CM) will produce higher response (abstinence) rates than initial treatment that combines standard Drug Counseling with CM (DC+CM).
 - 1.a. To determine if pretreatment EA level moderates the effects of ACT+CM on initial response. It is hypothesized that the benefit of ACT+CM over DC+CM on initial response (abstinence) rates will be greater in the subgroup of individuals with higher pretreatment EA scores.
 - 1.b. To determine if the effects of ACT+CM are mediated by changes in EA and reward sensitivity. It is hypothesized that ACT+CM effects on initial treatment response will be mediated by the primary hypothesized treatment mechanisms, EA and reward sensitivity.

Secondary Aims/Hypotheses:

2. To determine the best sequencing of treatment for initial non-responders. For initial non-responders, it is hypothesized that continued ACT+CM treatment with pharmacotherapy (modafinil) augmentation will be most effective in promoting abstinence relative to treatment combinations involving DC and/or placebo.
3. To determine the best sequencing of treatment for initial responders. For initial responders, it is hypothesized that continued ACT+CM will be more effective (higher abstinence rates; < 46% relapse rate) than continued DC+CM.

Study Design

Overall Research Strategy. We propose an adaptive, two-stage SMART design to test the primary research hypothesis that ACT, when used in combination with CM, will increase initial treatment response rates. Secondary hypotheses will determine the probability of benefit associated with two sequences of treatments, specifically, continued ACT+CM for initial treatment responders (dashed lines in **Figure B.3.2.i**) and continued ACT+CM with modafinil augmentation for initial treatment non-responders (double lines in **Figure B.3.2.i**).

Overview of Study Design. Note: SR=stratified randomization; R=randomization; ACT=Acceptance and Commitment Therapy; DC=Drug Counseling; CM=Contingency Management; PLA=placebo; MOD=modafinil. Abstinent=6 consecutive (2 wks) cocaine-negative (BE<150 ng/ml) urines samples.

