Eligibility criteria (described above) will be evaluated as part of the General Evaluation protocol for all treatment research studies at our clinic. All potential subjects are invited to first participate in this

separate CPHS-approved protocol (**HSC-MS-05-0322 - "General Evaluation of Eligibility for Substance Abuse/Dependence Research**). Intake evaluation procedures will include a complete psychiatric diagnosis using the Structured Clinical Interview for DSM-5 (SCID-5) administered by trained licensed professional counselors under the supervision of a licensed clinical psychologist. Medical screening will include a history and physical examination, a blood draw for serum chemistry and blood count, urine sample for urinalysis and an electrocardiogram (EKG), and urine testing for drugs of abuse and pregnancy. Lab tests will include a Comprehensive Metabolic Panel (CMP) with tests of liver enzymes: alkaline phosphatase (ALP), alanine amino transferase (ALT), aspartate amino transferase (AST), Prothrombin time (PT), partial thromboplastin time (PTT), and bilirubin. We will apply the Child-Pugh criteria to exclude subjects with stage B or C scores, indicating severe liver disease. Upon completion of this intake evaluation, eligible participants will be invited to participate in the current study.

Study Site, Recruitment, Projected Enrollment. The study site is the Treatment Research Clinic of the Center for Neurobehavioral Research on Addictions (CNRA), a university-supported center of excellence within the UT-Houston Department of Psychiatry and Behavioral Sciences and a NIDA-funded Medications Development Center (P50 DA 009262). Since 1995, the CNRA has been the site for more than 20 randomized clinical trials, enrolling over 1,000 patients with substance use disorders, most of these with CUD. Established and effective recruitment strategies have been identified ³⁷ and will be used, including newspaper/newsletter articles, public service announcements on TV and radio, notices mailed to local professionals, and billboards located throughout the local community. We will reach our projected enrollment of N=160 subjects within 40 months, based on our established record of enrolling 4 new subjects per month on average; a rate we have maintained for the past 5 years.

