Phase 1 treatments. Consenting subjects will be assigned to one of the two 4-week Phase 1 treatments, ACT+CM or DC+CM, using urn randomization to ensure balance between groups on baseline EA level, coded as "high" if AIS score > 45, or "low"≤ 45. Subjects in both treatments will be scheduled to attend three clinic visits per week (MWF) during the 4-week period. **Two** of these weekly visits will include 1-hour therapy sessions (ACT or DC).

Acceptance and Commitment Therapy-Cocaine Use (ACT). The overarching goal of ACT is to decrease experiential avoidance while increasing acceptance and willingness to experience unpleasant thoughts, feelings, and physical symptoms. More specifically, ACT will assist cocaine patients to notice their internal cravings and triggers, abandon their attempts to manage these triggers via active avoidance, suppression or other control-based strategies, and to make commitments to engage in behaviors consistent with their chosen values or goals. ACT encourages clients to experience thoughts and feelings from an observer perspective, and helps them not to believe distressing thoughts and feelings as if they are literally true and in need of action. ACT treatment will be based on the therapy manual developed and tested previously.^{38, 39} The manual covers 10 core topics listed in **Table B.3.2.vi.** Our experienced ACT therapists will be taught to use the manual as a map with flexibility to "go with the client" so long as issues of acceptance, diffusion, values, and committed action are thoroughly covered. Mindfulness exercises, metaphors, and homework sheets will be used to pursue therapeutic goals, more so than didactic instruction. Masters-level therapists with ACT experience from our previous trial ³⁸ will be trained and supervised by [name] (Co-I) and [name] (Consultant).

Drug Counseling (DC). We will use the manual-guided individual DC modeled after the NIDA Collaborative Cocaine Treatment Study ⁴⁰ and used as the active control therapy in our previous studies.^{38, 41, 42} DC approximates clinical practice as it is considered the most common type of evidence-

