based treatment in the community for patients actively using cocaine. DC educates patients about important concepts in addiction recovery based on the underlying philosophy that physical, emotional, spiritual, and interpersonal needs must all be addressed to support recovery. Accordingly, the DC manual covers the core topics listed in **Table B.3.2.vi**. Masters-level therapists with DC experience from our previous trials^{41, 42} will be trained and supervised by [name] (Co-I).

Contingency Management (CM). We will use the same high-magnitude CM schedule shown previously to be feasible and effective in facilitating initial cocaine abstinence.¹² Subjects will earn vouchers for cocaine-negative urine samples collected at scheduled clinic visits (MWF) each week. Under an escalating reinforcement schedule, voucher values will begin at \$15 and increase by \$10 for each consecutive negative urine. Provision of a cocaine-positive urine or failure to provide a scheduled sample will result in no vouchers earned and will reset the schedule to the initial value (\$15). Bonus vouchers (\$10) will be given for completing all study-related tasks in a given week. Subjects will redeem their earned vouchers for cash loaded to the ClinCard, a reloadable debit card.

Initial response and re-randomization. Following Phase 1 treatment, the primary outcome of response/non-response will be determined. Subjects who submit 6 consecutive (2 weeks) cocaine negative urine samples by week 4 will be classified as responders. Those who fail to meet response criteria will be classified as non-responders.

During second (Phase 2) treatment:

- Responders will continue to receive their assigned initial treatment, as described below.
- Non-responders in each initial treatment arm will be re-randomized to a second treatment consisting of pharmacotherapy augmentation with either modafinil or placebo.

All subjects will attend three clinic visits per week (MWF) during the 8 week second treatment period.

Table B.3.2.vi. 10 Core Topics for ACT and DC

Second (Phase 2) treatments	ACT	DC
Continued ACT or DC. Twice weekly 1-hour ACT and DC sessions will continue during the 8 weeks of second treatment, covering the core topics shown in Table B.3.2.vi.	Preparing to begin	Planning my recovery
	Values	Stages of recovery
	Making contact with the cost of using	People, places, things
	Creative hopelessness	Self-help groups & support systems
	Control v Willingness	Establishing a support system

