Experiential Avoidance: The *Avoidance and Inflexibility Scale (AIS)* is a 13-item self-report measure, on which respondents indicate, using a 5-point Likert-style scale, their level of avoidance and inflexibility with regard to internal experiences. The AIS has been adapted for several substance-using and other populations,^{38, 48} and in our previous study was modified for cocaine users. Higher scores indicate more avoidant and inflexible responses to internal states associated with cocaine use. The internal consistency of the AIS in our past studies was .89. The AIS will be used as the stratification variable for initial randomization. High avoidance will be defined as AIS scores > 45, based on our preliminary data, showing that this cutoff score distinguished CM responders from non-responders with good sensitivity and specificity indices. The *Acceptance and Action Questionnaire for Substance Abuse (AAQ-SA)* is an 18-item self-report measure on which respondents rate their urges on a 7-point Likert-type scale (1 = “never true” to 7 = “always true”). The AAQ is the standard measure of psychological flexibility. The AAQ-SA is the substance abuse focused version of this measure and has demonstrated good internal consistency, factor structure, and construct validity.¹⁰² The *Valuing Questionnaire (VQ)* is a 10-item self-report measure that assesses the effectiveness of ACT interventions using a 6-point Likert-type scale (1 = “Not at all true” to 6 = “Completely true”). The VQ should provide ACT researchers a convenient, reliable, valid measure for evaluating ACT interventions.¹⁰³ The *Five Facet Mindfulness Questionnaire (FFMQ)* is a 39-item self-report consisting of five subscales (observing, describing, acting with awareness, non-judging of inner experience, and non-reactivity to inner experience) that assess a participant’s mindfulness based on a 5-point Likert-type scale (1 = “Never or very rarely true” to 5 = “Very often or always true”). Mindfulness facets have been found to be significantly related to meditation experience, psychological symptoms and well-being.¹⁰⁴ The *PTSD checklist (PCL-5)* is a 20-item self-report checklist of traumatic events, PTSD symptoms and severity rated on a 5-point Likert-type scale (0 = “Not at all” to 4 = “Extremely”) and will be used to assess new or worsening trauma symptoms. The *Distress Tolerance Scale (DTS)* is a 15-item self-report measure on which respondents indicate, on a 5-point Likert-type scale (1 = “strongly agree” to 5 = “strongly disagree”), the extent to which they believe they can experience and withstand distressing emotional states (e.g., “I can’t handle feeling distressed or upset”). The internal consistency of the DTS is $\geq .82$.⁴⁹ A *Cold Pressor Task (CPT)* will be implemented as an index of physical distress tolerance, otherwise conceptualized as EA of physical distress.⁵⁰ This task involves continual application of a cold stimulus, intended to be safe but aversive, to the hand up to the wrist. Consistent with prior work, we will use ice water (1°C; 33°F) and instruct participants to keep hands still while submerged.⁵¹ Pain threshold is defined as the length of time (in sec) until a self-report of pain is made by the participant. Tolerance is defined as the length of time (in sec) until participant reports that the pain or discomfort is no longer tolerable and/or spontaneous termination of the procedure. Endurance is defined as tolerance minus threshold.⁵² It should be noted that, in the absence of gold standard self-report or behavioral measures of experiential avoidance or emotional tolerance, the measures selected have shown the most relevance to the mechanisms of interest in the present study based on past work.

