Hyp. 1.a. The benefit of ACT+CM over DC+CM on initial response (abstinence) rates will be greater in the subgroup of individuals with higher pretreatment EA scores. Adding the interaction term (EA-by treatment) to the logistic regression model will evaluate the moderating effect of EA.

Hyp. 1.b. ACT+CM effects on initial treatment response will be mediated by the primary hypothesized treatment mechanisms, EA and reward sensitivity. In the context of the direct effect of treatment on response, mediational modeling will evaluate the *indirect* effect of treatment on response via EA and reward sensitivity variables, using the product moment method with bootstrapped 95% CI and Bayesian posterior distributions.

Hyp. 2. For initial non-responders, continued ACT+CM treatment with pharmacotherapy (modafinil) augmentation will be most effective in promoting abstinence relative to treatment combinations involving DC and/or placebo. Logistic regression will evaluate cocaine abstinence at the end of second treatment in a set of contrasts: (1) modafinil versus placebo within each initial treatment; (2) the sequence of ACT+CM with modafinil augmentation versus DC+CM with modafinil augmentation.

Hyp. 3. For initial responders, continued ACT+CM will be more effective (higher abstinence rates; < 46% relapse rate) than continued DC+CM. Logistic regression will evaluate cocaine abstinence/relapse at end of second treatment as a function of initial treatment (ACT+CM vs DC+CM).

Power. Power estimates for Hypotheses 1, 2 and 3 will use as the primary outcome (i.e., “response”), two consecutive weeks of cocaine abstinence (BE ≤ 150 ng/mL). Initial treatment response (abstinence) rates are expected to be $\sim 40\%$, based on our previous study¹² and pooled data across cocaine clinical trials⁸⁵; however we predict a difference in response rates, favoring ACT+CM over DC+CM by about 20%, constituting a clinically meaningful treatment effect. Among initial non responders, we expect at least a

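### Baseline experiential avoidance is neither balanced at the modafinil/placebo re-randomization nor adjusted for in the Hyp. 2 model: a small, avoidable loss of precision, and a possible systematic difference in the cross-arm contrast

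*Combined protocol and SAP*

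**What the plan says.** **First randomization.** Under Phase 1 treatments, patients are assigned "using urn randomization to ensure balance between groups on baseline EA level", split at an AIS score of 45. The Experiential Avoidance text in the Assessment Schedule gives the reason: in preliminary data "this cutoff score distinguished CM responders from non-responders with good sensitivity and specificity indices". It also sets the scope: "The AIS will be used as the stratification variable for initial randomization".

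**Second randomization.** Under Initial response and re-randomization: "Non-responders in each initial treatment arm will be re-randomized to a second treatment consisting of pharmacotherapy augmentation with either modafinil or placebo". No method, ratio or balancing factor follows. The legend to the design overview reads "Note: SR=stratified randomization; R=randomization". That fits a stratified first step and a plain second one, but the figure itself is not available.

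**Model.** For Hyp. 2, "Logistic regression will evaluate cocaine abstinence at the end of second treatment in a set of contrasts": modafinil versus placebo within each initial treatment, then ACT+CM with modafinil versus DC+CM with modafinil. No covariate is named. EA enters a model only as a moderator (Hyp. 1.a) and a mediator (Hyp. 1.b). The Analytic strategy adds inverse probability weights for the re-randomization but does not say that they use EA.

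**The concern.** The plan protects EA balance where groups are largest, about 80 per arm, and drops that protection where they are smallest. Phase 2 non-responders are again reinforced for cocaine-negative urines, so by the protocol's own rationale EA could still be prognostic for them. If it is, a chance EA difference between modafinil and placebo cells moves the estimate and is neither prevented nor adjusted for. The Summary under Power accepts a posterior probability of benefit above 0.80 as enough for a Go decision, so a shift of a few points can matter.

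The cross-arm contrast raises a separate issue. Its two groups are what remains of each arm after responders have been removed, and response is an outcome of the treatment being compared.

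**Working it through.** **Plan's own figure.** Table B.3.2.x gives power of 0.81 for contrasts 5 vs 6 (difference 0.17) and 7 vs 8 (difference 0.13) at a posterior threshold of 0.80. I take these to be the two within-arm modafinil contrasts. The cell rates are in a figure that is not shown, so the value cannot be reproduced cleanly. With 24 per cell and a difference of 0.17, a normal approximation reaches about 0.81 only near 5% placebo abstinence. The calculations below therefore compare analyses with and without EA and do not lean on the stated 0.81.

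**Step 1: cell sizes.** Inputs are N = 160, 80 per arm and 1:1 re-randomization (both ratios assumed), "Initial treatment response (abstinence) rates are expected to be" about 40%, and a 20-point advantage for ACT+CM. Cell size = 80 × (1 − response) / 2.
- If 40% is the DC rate (40% vs 60%): 80 × 0.60 / 2 = 24 and 80 × 0.40 / 2 = 16.
- If 40% is the average (30% vs 50%): 80 × 0.70 / 2 = 28 and 80 × 0.50 / 2 = 20.

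**Step 2: chance imbalance.** Let h be the high-EA share among non-responders, assumed 0.60 to 0.70. The SD of the difference in high-EA share between two cells is √(2h(1−h)/n).
- n = 16, h = 0.60: √(0.48/16) = 17 points.
- n = 28, h = 0.70: √(0.42/28) = 12 points.

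The exact binomial chance of a gap of 20 points or more, over h = 0.60 to 0.70:

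| n per cell | Chance |
|---|---|
| 16 | 17–21% |
| 20 | 23–26% |
| 24 | 15–18% |
| 28 | 11–13% |

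The chance does not fall steadily with n, because 20 points means 4 patients at both n = 16 and n = 20. Splitting a fixed pool exactly in half gives a more uneven 8 to 33%, for the same reason of discreteness.

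**Step 3: shift in the estimate.** Shift = imbalance × g, where g is the assumed difference in Phase 2 abstinence between EA strata. A 20-point imbalance moves the difference by 2, 4 or 6 points for g = 10, 20 or 30. At g = 20 points the SD of the shift is 0.20 × 12 to 17 = about 2.4 to 3.5 points.

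**Step 4: what adjustment recovers.** Unadjusted variance = [p0(1−p0) + p1(1−p1)]/n. EA component = 2h(1−h)g²/n. Power = Φ(d/SE − 0.84), a one-sided equivalent of the 0.80 threshold. Take p0 = 0.25 (assumed), d = 0.17 and h = 0.50, where the EA component is largest. At n = 16 the variance is (0.1875 + 0.2436)/16 = 0.0269, so SE = 0.164. With g = 0.20 the EA component is 0.5 × 0.04/16 = 0.00125, or 4.6% of that variance, and SE falls to 0.160.

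| n per cell | Power unadjusted | g = 0.10 | g = 0.20 | g = 0.30 |
|---|---|---|---|---|
| 16 | 0.577 | 0.579 | 0.587 | 0.600 |
| 24 | 0.665 | 0.668 | 0.676 | 0.691 |
| 28 | 0.701 | 0.704 | 0.713 | 0.728 |
| Variance removed | – | 1.2% | 4.6% | 10.4% |

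At h = 0.65 the reductions are 1.1%, 4.2% and 9.5%.

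**Step 5: cross-arm contrast.** An illustration with assumed rates: 60% high EA at entry; DC+CM response 50% in low EA and 30% in high EA; ACT+CM response 60% in both, which is the pattern Hyp. 1.a predicts.
- DC+CM non-responders: low 0.40 × 0.50 = 0.20, high 0.60 × 0.70 = 0.42; high-EA share 0.42/0.62 = 68%.
- ACT+CM non-responders: low 0.40 × 0.40 = 0.16, high 0.60 × 0.40 = 0.24; high-EA share 0.24/0.40 = 60%.

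The gap of about 8 points is expected, not chance. At g = 0.20 it shifts the contrast by about 0.08 × 0.20 = 1.6 points in favor of ACT+CM. Balancing the second randomization within each arm leaves it untouched.

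**The case against.** The strongest reply is that a valid randomized comparison needs no covariate balance. Modafinil versus placebo is randomized within arm, chance imbalance is part of the sampling error, and the posterior width already reflects it. That stands. A reader might infer that leaving EA out biases these contrasts; the design does not support that.

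A reader might also infer noise on the scale of the planned modafinil effect. It is not: an SD of about 2.4 to 3.5 points at a 20-point EA difference compares with planned effects of 13 to 17 points and a standard error of about 12 to 16 points. The main limit on Hyp. 2 is cell size, which adjustment barely changes.

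It is fair, too, that the evidence on EA is modest. The Background Information reports a post-hoc comparison of 99 patients, concerns Phase 1 response, and names intake urine status as an already known marker. EA is thus a modifiable predictor on which the protocol relies, and the documents do not establish it as the main one. Phase 2 patients have already failed to respond, one arm has had four weeks of therapy aimed at EA, and the reinforcement schedule changes. An EA effect on Phase 2 abstinence is therefore an assumption.

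The reply does not reach the cross-arm contrast, because re-randomization within arm does not make those two groups comparable.

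**Conclusion.** The omission is real and its consequence is small. For modafinil versus placebo within arm, the plan forgoes about 1 to 10% of the variance, or roughly 0 to 3 points of power. This rests on 16 to 28 per cell, 25% placebo abstinence and a 10 to 30 point EA difference in Phase 2 abstinence; the last two are assumptions. EA imbalance of 20 points or more would arise in about 11 to 26% of trials at 60 to 70% high EA, also assumed. The planned cell sizes are in a figure that is not shown, and the 16 to 28 range covers both readings of the 40% response rate.

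For ACT+CM+modafinil versus DC+CM+modafinil, an EA difference may be systematic, but only if Hyp. 1.a holds and EA still matters in Phase 2. There the covariate does more than reduce noise. This is an inexpensive improvement, not a flaw that undermines Hyp. 2.

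**What to change.** Pre-specify baseline AIS as a covariate in the Hyp. 2 logistic model for all contrasts. Use the pretreatment score, since later scores are affected by the assigned therapy. Because Table B.3.2.x appears to state effects as differences in proportions, say that adjusted differences will be obtained by averaging model predictions over the observed AIS distribution. State also that, in the cross-arm contrast, adjustment deals only with measured baseline EA and not with other effects of selecting on non-response.

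State the method and ratio of the second randomization. Optionally, for patients not yet re-randomized, balance it on AIS > 45 within initial arm using the existing urn procedure.

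The cost is one extra parameter in a small model. AIS is already collected before treatment, and the covariate can be added even if re-randomization is complete. No visit, treatment or eligibility rule changes.
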